### **11.2. Sample Size Determination**

As this is an exploratory, hypothesis-generating study, no formal statistical hypothesis testing will be performed.

The adequacy of the sample size for the different parts of the study has been assessed by evaluating the performance of the planned analyses on the primary endpoint (mean HBsAg change from baseline at Week 24) comparing JNJ-56136379+NA with placebo+NA as outlined in Section 11.3. Baseline is defined as the last assessment prior to the first intake of study drugs (JNJ-56136379/NA/placebo) on Day 1.

Power was assessed using simulations (10,000 replicates per scenario) with means and SDs for the placebo+NA and JNJ-56136379+NA arms as listed in Table 7. Mean and SD may depend on HBeAg status at baseline and prior treatment (currently not being treated or virologically

suppressed). Treatment with JNJ-56136379 was set to result in one additional mean  $\log_{10}$  IU/mL decline in HBsAg from baseline at Week 24. Data were simulated from mixture distributions which reflect the skewed distributions which are typical HBsAg decline data. It is assumed that HBeAg-positive subjects will enroll slower than HBeAg-negative subjects, particularly in virologically suppressed subjects. Therefore, the aim is to have at least 40% HBeAg-positive subjects currently not being treated and 30% HBeAg-positive virologically suppressed subjects.

For the dose-response modeling (multiple contrast test) the placebo+NA arms of Parts A and B will be pooled and the HBeAg subgroups will be pooled per dose. Assuming the treatment effect does not depend on HBeAg status, the power to detect a dose-response signal ( $\alpha=0.10$ , one-sided) depends on the assumed effect of the low dose: ranging from 91% when the low dose has no effect to 99% when the low dose has the same effect as the high dose. Sensitivity analyses will be done investigating differences across Parts A and B and differences between the two HBeAg subgroups.

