#### **5.4. Dose response Analysis**

The dose-response of the effect of JNJ-56136379 in an NA background regimen on the Week 24 HBsAg change from baseline will be studied using the combined data of Part A and Part B. The data will consist of three dose groups:

- Placebo: pooled control arms of Part A and Part B
- Low Dose (75 mg): JNJ-56136379+NA arm of Part A
- High Dose (to be determined): JNJ-56136379+NA arm of Part B

The dose-response analysis will be carried out by subject population (currently not treated or virologically suppressed by current NA treatment), irrespective of HBeAg status, and also by HBeAg status within each population.

The presence of a dose-response signal will be assessed using a multiple contrast test, following the MCP-Mod methodology (REF: Bjornkamp et al. 2009). In this approach, a candidate set of plausible dose-response shapes need to be defined. As only 2 JNJ-

---

[figure not shown]
56136379 doses (and placebo) are studied in the current trial, possible dose-response shapes to consider are determined by the relative effect of the low dose compared to the high dose and the spacing of the dose. Three monotone dose-response shapes are included in the candidate model set:

- Linear
- Emax: the effect of the low dose is higher than expected from a linear relationship
- Exponential: the effect of the low dose is less than expected from a linear relationship

These models are parametrized as follows (using notation as in Bornkamp et al., 2009):

- Linear model (no parameters)
- Emax ( $ED_{50}=0.20$ )
- Exponential ( $\delta=0.18$ )

The three dose response shapes are illustrated in Figure 1.

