**Figure X2: Multiple Contrast Test Candidate Model Set**

The significance of the dose-response signal associated with each candidate model will be determined using trend tests with model-specific optimal contrast coefficients. The maximum of the candidate model trend test statistics will be used to evaluate the presence of a dose-response signal, properly accounting for multiplicity at an overall level of 5% (1-sided) using MCP-Mod methodology.

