### **Multiple Contrast Test**

The MCT will be executed using the MCTtest-function of the R-package DoseFinding (version 0.9-16) using the R code (See **APPENDIX 2**). In this code, the low dose is expressed relative to the high dose. At the time of execution, the scalar “dose.rat” will be replaced by ratio of the low dose over the high dose.

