#### Input:

1. mean.placebo = mean Week 24 HBsAg change from baseline in the placebo-group (arms pooled over Part A and Part B).
2. mean.low.dose = mean Week 24 HBsAg change from baseline in the JNJ379+NA group of |Part A
3. mean.high.dose = mean Week 24 HBsAg change from baseline in the JNJ379+NA group of |Part B
4. se.mean.placebo = standard error of the mean Week 24 HBsAg change from baseline in the placebo-group (arms pooled over Part A and Part B)
5. se.low.dose = standard error of the mean Week 24 HBsAg change from baseline in the JNJ379+NA group of Part A
6. se.high.dose = standard error of the mean Week 24 HBsAg change from baseline in the JNJ379+NA group of Part B

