## APPENDIX 2: R CODE FOR DOSE RESPONSE

```
library(DoseFinding)
dose.range=c(0,dose.rat,1)
models=Mods (linear=NULL,emax=0.20,exponential=0.18,doses=c(dose.r
ange),maxEff=1,placEff=0)
optContr (models,w=c (2/8,3/8,3/8))

library(DoseFinding)
dose.range=c(0,dose.rat,1)
models=Mods (linear=NULL,emax=0.20,exponential=0.18,doses=c(dose.r
ange),maxEff=1,placEff=0)
optContr (models,w=c (2/8,3/8,3/8))
MCTtest (dose=dose.range,models=models,type="general",resp=c (mean.
placebo,mean.low,mean.high),S=matrix (nrow=3,ncol=3,c (se.mean.plac
ebo^2,0,0,0,se.mean.low^2,0,0,0,se.mean.high^2))
```

---

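### The dose-response test is given estimated standard errors but no degrees of freedom, so its stated 5% level is not held in the small HBeAg-positive analyses

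*SAP*

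**What the plan says.** SAP 5.4 looks for a dose-response signal with the largest of three contrast statistics (linear, Emax, exponential), "properly accounting for multiplicity at an overall level of 5% (1-sided) using MCP-Mod methodology". Each subject population is analysed "irrespective of HBeAg status, and also by HBeAg status within each population".

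The software is fixed: "The MCT will be executed using the MCTtest-function of the R-package DoseFinding (version 0.9-16"). The Input list in SAP 5.4 has six items, three group means and three standard errors, for example "se.mean.placebo = standard error of the mean Week 24 HBsAg change from baseline in the placebo-group (arms pooled over Part A and Part B"). No degrees of freedom or group sizes are listed.

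The call in SAP Appendix 2 matches that list: "MCTtest (dose=dose.range,models=models,type='general", followed by the three means and a 3×3 diagonal matrix of squared standard errors. Neither SAP 5.4 nor Appendix 2 mentions a t distribution. By contrast, the MMRM code for the same endpoint in SAP Appendix 3 asks for Kenward-Roger degrees of freedom.

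**The concern.** A standard error estimated from a handful of subjects is itself uncertain. A t reference allows for that and a normal reference does not. With only means and squared standard errors as input, the call holds nothing from which a t reference could be built. The critical value is then too small, and false signals occur more often than the plan says.

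The effect grows as the groups shrink. The by-HBeAg analyses are the smallest in the plan, and in the HBeAg-positive ones each standard error rests on 6 to 12 subjects. At stake is whether a signal reported there at a nominal 5% carries that error rate.

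**Working it through.** **Inputs**
- Doses relative to 250 mg: 0, 75/250 = 0.30, 1.
- Shapes from Appendix 2, scaled to 1 at the high dose. Linear: 0, 0.30, 1. Emax with ED50 0.20: (0.3/0.5) × 1.2 = 0.72 at the low dose. Exponential with delta 0.18: (e^1.667 − 1)/(e^5.556 − 1) = 0.017 at the low dose.
- Group sizes from Protocol Table 7, with placebo doubled because it is pooled over Parts A and B. Not treated: HBeAg-positive 8/12/12, HBeAg-negative 12/18/18. Suppressed: HBeAg-positive 6/9/9, HBeAg-negative 14/21/21. Either population with HBeAg pooled: 20/30/30.
- SDs from Table 7: placebo 0.4 (0.6 if not treated and HBeAg-positive), active 2.16. Equal SDs were run as well.

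**Hand check, one contrast (250 mg versus placebo, 6/9/9, SDs 0.4 and 2.16)**
- v0 = 0.16/6 = 0.0267; v2 = 4.6656/9 = 0.5184.
- Satterthwaite df = (v0 + v2)² / (v0²/5 + v2²/8) = 0.2971/(0.00014 + 0.03359) = 8.8.
- P(t with 8.8 df > 1.645) = 6.8%, against the nominal 5%.
- The same steps at 20/30/30 give v0 = 0.0080, v2 = 0.1555, df = 31.9 and 5.5%.

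The maximum of three contrasts needs a critical value further out in the tail, so simulation is used for the full test.

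**Calibration**
- With known standard errors the simulated level is 4.9–5.1% in every cell, so the engine returns the nominal level.
- The protocol's planned power, at a one-sided 10%, is "ranging from 91% when the low dose has no effect to 99% when the low dose has the same effect as the high dose". The coded procedure (separate standard errors, normal critical values) at 20/30/30 gives 90.2% and 98.2%. That run used the planning SDs and an assumed two-component mixture, because Protocol 11.2 does not give the mixture parameters. The plan's figures are reproduced to within about a point.

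**Level as coded, nominal one-sided 5%, normal data with no effect**

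| Analysis | Level |
|---|---|
| Suppressed HBeAg-positive 6/9/9, contrasts optimised on S | 7.6–8.3% |
| Not treated HBeAg-positive 8/12/12, contrasts optimised on S | 6.7–7.8% |
| Both HBeAg-positive cells, contrasts fixed at 2/8, 3/8, 3/8 | 6.2–7.3% |
| HBeAg-negative cells, contrasts optimised on S | 6.0–6.3% |
| HBeAg pooled 20/30/30 | 5.4–6.7% |

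Ranges cover equal and planning SDs and simulations of different size. The largest (100,000 null trials per cell, contrasts optimised on S) gives 7.6–7.8% at 6/9/9, 6.7–7.0% at 8/12/12 and 5.6–5.9% pooled.

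**Departure from normality, HBeAg-positive sizes, signals counted toward decline**
- Exponential skew, equal SDs: 9.5–10.1% with the long tail toward decline, 5.9–6.4% with the opposite tail.
- Skew toward decline, SDs 0.4/2.16/2.16: about 3% or slightly less, which is below nominal.

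These are examples, not bounds.

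**Level after a correction, HBeAg-positive cells, normal data**
- df = N − 3 with separate standard errors: 5.9–6.9%.
- Smallest Satterthwaite df across the three contrasts: about 5.3–6%.

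**The case against.** A reader might infer that the test simply runs at 7 to 8%. The documents do not support that as a fact.
- The figure needs normal data, and Protocol 11.2 expects skewed HBsAg changes. Under skew even the sign of the error is not fixed.
- It also needs contrasts re-optimised on each estimated covariance matrix. SAP 5.4 and the contrast code in Appendix 2 can equally be read as fixing the contrasts at the 2/8, 3/8, 3/8 weights, which gives a smaller excess.
- The group sizes are planned ones.

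A reader might also infer that the main dose-response result is compromised. Protocol 11.2 and 11.3.1 pool HBeAg status for this test and treat HBeAg differences as sensitivity analyses. At the pooled size the excess is small.

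The study is labelled exploratory, and no development decision is tied to this test in either document. That limits the consequence. It does not excuse a specific stated error rate that the code does not deliver.

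The printed call lacks its closing parenthesis, and its input names differ slightly from those in SAP 5.4, so it is a template. R was not available to confirm the function's default. But the Input list also omits degrees of freedom and group sizes, so the omission is not just a typing matter. SAP section 1 names a SAS procedure for dose-response modelling as well, but SAP 5.4 assigns this test to MCTtest.

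**Conclusion.** The point stands in a limited form. As specified, the dose-response test treats estimated standard errors as known, so the 5% level in SAP 5.4 is not delivered in the small by-HBeAg analyses. With normal data at the planned sizes the excess in the HBeAg-positive cells is roughly 1 to 3 percentage points, depending on the cell and on how the contrasts are set. It is about half a point to under 2 points with HBeAg pooled. The mechanism follows from the inputs listed in the SAP. The exact size rests on normality, the planned group sizes and the choice of contrasts. Skewness and unequal variances can matter as much as the missing degrees of freedom, and they are a separate limitation. The plan should be corrected, but this does not invalidate the pooled analysis.

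**What to change.** In SAP Appendix 2, add the df argument to the MCTtest call. Set it to the smallest Satterthwaite degrees of freedom across the three contrasts, computed from the arm variances and sizes, and list those sizes under Input in SAP 5.4. Do not use N − 3 with separate standard errors, because part of the excess remains.

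In SAP 5.4, state that critical values come from the multivariate t and that the 5% level is approximate in the HBeAg subgroups. Also say whether the contrasts are fixed at the 2/8, 3/8, 3/8 weights or recomputed from the estimated covariance.

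The cost is one argument, a short df calculation and a few sentences. Critical values become slightly larger and power slightly lower. Nothing changes for subjects or data collection. The change does not address skewness.

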### APPENDIX 3: SAS CODE FOR THE MMRM MODEL

```
proc mixed data=mod01 (where = (paramcd = 'LGHBSAG' ));  
  by hbeagstat;  
  class avisitn trtlon usubjid;  
  model chg = avisitn trtlon trtlon*avisitn / ddfm=kr2;  
  repeated / type=UN subject=usubjid ;  
run;
```

hbeagstat = HBeAg status at baseline

avisitn = analysis visits

trtlon = Treatment groups

usubjid = subject ID

chg = change from baseline

In case the above leads to convergence issues, alternative within-subject covariance structures will be considered, in the following hierarchy:

```
proc mixed data= mod01 maxopt=1000;  
  by hbeagstat;  
  class avisitn trtlon usubjid;  
  model chg= avisitn trtlon trtlon*avisitn /dist=normal link=identity solution ddfm=kr2;  
  random intercept/subject=usubjid v vcorr;  
  random _residual_ /type=ante(1) subject=usubjid g gcorr;  
  covtest 'int' general 1 0 0 0 0 0 0 0 0 0 0 0 0 0 0 0;  
  covtest 'all var equal' general  
    0 1 -1 0 0 0 0 0 0 0 0 0 0 0 0 0,  
    0 0 1 -1 0 0 0 0 0 0 0 0 0 0 0 0,  
    0 0 0 1 -1 0 0 0 0 0 0 0 0 0 0 0,  
    0 0 0 0 1 -1 0 0 0 0 0 0 0 0 0 0,  
    0 0 0 0 0 1 -1 0 0 0 0 0 0 0 0 0,  
    0 0 0 0 0 0 1 -1 0 0 0 0 0 0 0 0,  
    0 0 0 0 0 0 0 1 -1 0 0 0 0 0 0 0;  
  covtest 'all corr equal' general  
    0 0 0 0 0 0 0 0 0 1 -1 0 0 0 0 0,  
    0 0 0 0 0 0 0 0 0 0 1 -1 0 0 0 0,  
    0 0 0 0 0 0 0 0 0 0 0 1 -1 0 0 0,  
    0 0 0 0 0 0 0 0 0 0 0 0 1 -1 0 0,  
    0 0 0 0 0 0 0 0 0 0 0 0 0 1 -1 0,  
    0 0 0 0 0 0 0 0 0 0 0 0 0 0 1 -1;  
  covtest 'all var&corr equal' general  
    0 1 -1 0 0 0 0 0 0 0 0 0 0 0 0 0,  
    0 0 1 -1 0 0 0 0 0 0 0 0 0 0 0 0,  
    0 0 0 1 -1 0 0 0 0 0 0 0 0 0 0 0,  
    0 0 0 0 1 -1 0 0 0 0 0 0 0 0 0 0,  
    0 0 0 0 0 1 -1 0 0 0 0 0 0 0 0 0,  
    0 0 0 0 0 0 1 -1 0 0 0 0 0 0 0 0,
```

---

```

0      0 0 0 0 0 1 -1    0 0 0 0 0 0,
0      0 0 0 0 0 0 0      1 -1 0 0 0 0,
0      0 0 0 0 0 0 0      0 1 -1 0 0 0,
0      0 0 0 0 0 0 0      0 0 1 -1 0 0,
0      0 0 0 0 0 0 0      0 0 0 1 -1 0,
0      0 0 0 0 0 0 0      0 0 0 0 1 -1 0,
0      0 0 0 0 0 0 0      0 0 0 0 0 1 -1;
run;

proc mixed data= mod01 maxopt=1000;
by hbeagstat;
class avisitn trtlon usubjid;
model chg= avisitn trtlon trtlon*avisitn /dist=normal link=identity solution ddfm=kr2;
random intercept/subject=usubjid v vcorr;
random _residual_ /type=arh(1) subject=usubjid g gcorr;
covtest 'int' general 1 0 0 0 0 0 0 0 0;
covtest 'corr' general 0 0 0 0 0 0 0 0 1;
covtest 'all var equal' general
      0      1 -1 0 0 0 0 0 0 ,
      0      0 1 -1 0 0 0 0 0 ,
      0      0 0 1 -1 0 0 0 0 ,
      0      0 0 0 1 -1 0 0 0 ,
      0      0 0 0 0 1 -1 0 0 ,
      0      0 0 0 0 0 1 -1 0 ,
      0      0 0 0 0 0 0 1 -1 ;
run;

proc mixed data= mod01 maxopt=1000;
by hbeagstat;
class avisitn trtlon usubjid;
model chg= avisitn trtlon trtlon*avisitn /dist=normal link=identity solution ddfm=kr2;
random intercept/subject=usubjid v vcorr;
random _residual_ /type=ar(1) subject=usubjid g gcorr;
output out=overdisp2 pearson=pearson;
covtest 'int' general 1 0 0;
covtest 'ar1' general 0 1 0;
covtest 'int&ar1' general 1 0 0, 0 1 0;
run;

```

For the pool analysis include HBeAg status as fixed effect in the above models

---

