**Part A:**

Approximately 70 subjects who are currently not being treated for their CHB infection will be randomized in a 3:1:3 ratio to receive one of the following treatments:

- Treatment Arm 1: JNJ-56136379 (N=30) (open-label)

After full recruitment, this treatment arm was discontinued early per Protocol Amendment 4. All subjects were to stop further dosing with JNJ-56136379 75 mg, start treatment with NA, and enter the post-treatment follow-up phase (Schedule 1).

- Treatment Arm 2: Placebo + NA (ETV or TDF) (N=10)
- Treatment Arm 3: JNJ-56136379 + NA (ETV or TDF) (N=30)

At the same time, approximately 40 subjects who are virologically suppressed by current NA treatment will be randomized in a 1:3 ratio to receive one of the following treatments:

- Treatment Arm 4: Placebo + NA (ETV or TDF) (N=10)
- Treatment Arm 5: JNJ-56136379 + NA (ETV or TDF) (N=30)

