### **11.3.3. Other Analyses**

Mean changes and maximum mean decrease from baseline in HBsAg, HBeAg, and HBV DNA levels over time will be tabulated by study treatment together with respective SDs. The proportion of subjects with seroclearance and seroconversion of HBsAg and HBeAg will also be tabulated by study treatment. The proportion of subjects with virologic response and the proportion of subjects with virologic or clinical relapse, defined as HBeAg, HBsAg, and/or HBV DNA levels below and above certain thresholds at different time points, respectively, will be categorized as detailed in the SAP, as applicable. Data will also be presented graphically by study phase, study treatment and by individual subject. All individual values will be presented in subject listings.

The least squares (LS) mean change from baseline in serologic parameters and HBV DNA for each study treatment and time point will be estimated with a repeated measurement model (mixed-effects model for repeated measures) including study treatment and time point as fixed effect. The model will allow for unequal variances between study treatments. A 95% confidence interval (CI) will be constructed around the difference between the LS mean of each study treatment. Other methods to evaluate the changes in serologic parameters and HBV DNA may include slope estimation, time-to-event or proportions of subjects who reach a certain level or who exceed a certain reduction.

The proportion of subjects with sustained reduction/suppression and/or sero-clearance, including but not limited to functional and partial cure, will be determined during follow-up. Single and multiple markers such as HBsAg, HBeAg, HBV DNA and ALT levels will be taken into consideration in this analysis.

Other efficacy endpoints, eg, HBV RNA and HBcrAg, will be analyzed descriptively. For continuous variables, descriptive statistics (n, mean, SD, median, minimum, maximum) will be calculated; mean difference and CIs may be calculated where appropriate and, if appropriate, a general linear mixed model will be used to compare the different study treatments. For categorical variables, frequency tables will be presented. Difference in proportions and CIs may be calculated where appropriate.

Analyses, tabulations and visualizations will be done for both treatment and follow-up phases.

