### **5. EFFICACY EVALUATIONS**

Efficacy assessments will be performed at the planned time points indicated in section 2.3 above (see Appendix 4, 5 and 6) using the ITT population. All HBV virology (i.e. HBV DNA and RNA) and serology (i.e. HBsAG, HBeAg, HbcAg, Anti-HBs, Anti-HBe) available data will be analyzed by subject population, hepatitis B e antigen (HBeAg) status

---

and overall, treatment group, analysis phase, analysis period and follow-up type and at each analysis time point (when applicable). Placebo treatments can be pooled as ‘placebo’ over Parts A and B. The sections below describe the data handling rules used in the primary, secondary and exploratory analysis.

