### **5.2.1 Analysis of the primary endpoint**

The following tabulation will be included:

- Descriptive statistics of the actual values (original unit and log10 transformed values) and the change from baseline (log10 transformed values) over time according to the specification described in section 2.6 will be included.
- Least Square (LS) means (SE) of change from baseline (and 95% confidence interval) per time point and overall based on log10 transformed values will be analyzed by subject population and part using mixed effects model for repeated measures. Also P-values for treatment, time, their interaction and overall will be added.
- LS means (SE) of change from baseline (and 95% confidence interval) per time point and overall based on log10 transformed values will be analyzed by subject population, part and by HBeAg status using mixed effects model for repeated measures. Also, P-values for treatment, time, their interaction and overall will be added.

---

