### 5.2.1.1 Mixed effects model for repeated measures

The main comparisons of interest in the efficacy analyses are:

- to evaluate the efficacy of 24 weeks of JNJ-56136379 monotherapy versus placebo+NA;
- to evaluate the efficacy of 24 weeks of JNJ-56136379+NA versus placebo+NA;
- to evaluate the efficacy of 24 weeks of JNJ-56136379 monotherapy versus JNJ-56136379+NA.

The primary endpoint, Week 24 HBsAg change from baseline, will be analyzed by a comparison of each dose of JNJ-56136379 added to the background NA therapy with the concurrent control arm (placebo + NA), within each of the 4 categories defined by subject population and HBeAg status:

- Low dose (75 mg) of JNJ-56136379+NA with placebo+NA (Part A) in currently not treated HBeAg positive subjects
- Low dose (75 mg) of JNJ-56136379+NA with placebo+NA (Part A) in currently not treated HBeAg negative subjects
- Low dose (75 mg) of JNJ-56136379+NA with placebo+NA (Part A) in virologically suppressed HBeAg positive subjects
- Low dose (75 mg) of JNJ-56136379+NA with placebo+NA (Part A) in virologically suppressed HBeAg negative subjects
- High dose (TBD) of JNJ-56136379+NA with placebo+NA (Part B) in currently not treated HBeAg positive subjects
- High dose (TBD) of JNJ-56136379+NA with placebo+NA (Part B) in currently not treated HBeAg negative subjects
- High (TBD) of JNJ-56136379+NA with placebo+NA (Part B) in virologically suppressed HBeAg positive subjects

---

- High (TBD) of JNJ-56136379+NA with placebo+NA (Part B) in virologically suppressed HBeAg negative subjects

The same comparisons versus placebo+NA as above will also be conducted with JNJ-56136379 monotherapy.

Change from baseline based on log10 transform for quantitative HBsAg, will be analyzed by subject population using mixed effects model for repeated measures [MMRM]) including treatment group, analysis time point (treated as discrete/categorical), their interaction, HBeAg status (in the pooled analysis only), as fixed effects. The covariance structure will include a random intercept at the level of the subject to capture between-subject variability, while within-subject variability will be captured with an unstructured (type=UN) covariance matrix. In case the latter leads to convergence issues, alternative within-subject covariance structures will be considered, in the following hierarchy:

- i) First-order ante-dependence structure (type=ANTE(1)),
- ii) Heterogeneous first-order autoregressive structure (type=ARH(1))

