### 5.2.1.3 Sensitivity Analysis

In addition, a similar analysis but without historical data in a frequentist approach will also be conducted as a sensitivity analysis for both part A and B using all population in ITT population at week 24 and will be conducted to compare:

- The mean of HBsAg change from baseline in log 10 transformed at week 24 of JNJ-56136379 monotherapy (open label) versus placebo+NA
- The mean of HBsAg change from baseline in log 10 transformed at week 24 of JNJ-56136379+NA versus placebo+NA
- The mean of HBsAg change from baseline in log 10 transformed at week 24 of JNJ-56136379 as monotherapy (open label) versus JNJ-56136379+NA

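### The SAP's repeated-measures model shares one covariance across arms where the protocol promised unequal variances; at the planning SDs this makes the JNJ+NA versus placebo+NA interval about 1.7 times too wide in virologically suppressed subjects

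*SAP*

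**What the plan says.** Protocol 11.3.3, on the repeated-measures model for serologic parameters and HBV DNA: "The model will allow for unequal variances between study treatments". The synopsis makes the same commitment.

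SAP 5.2.1.1 specifies a random subject intercept, and says that "within-subject variability will be captured with an unstructured (type=UN) covariance matrix". If that does not converge, the order is ANTE(1), ARH(1), AR(1). Treatment-specific variances are not mentioned.

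SAP Appendix 3 opens with "repeated / type=UN subject=usubjid" and then gives the three fallbacks. None has a group option, and each fallback adds one random intercept common to all arms. The ANTE(1) block confirms the layout: its contrasts have 16 columns (1 intercept, 8 variances, 7 correlations), so variances differ by visit and not by arm. The unstructured code has no random intercept although the SAP text asks for one; this does not affect the point.

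On what enters each fit, SAP 5.2.1 says the endpoint "will be analyzed by subject population and part using mixed effects model for repeated measures", and SAP 5.2.1.1 compares each dose "with the concurrent control arm (placebo + NA), within each of the 4 categories defined by subject population and HBeAg status".

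**The concern.** The protocol makes a specific commitment about variances and the SAP drops it without comment. The design is one where this matters. Planning puts the large SD on the active arm, and that arm has three times the subjects. A shared variance is therefore mostly the active arm's variance, and it is then charged to the small placebo arm, whose own spread is planned to be far smaller.

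The model supplies the LS-mean differences, SEs, p-values and 95% intervals that SAP 5.2.1 reports for Week 24 HBsAg change. The Bayesian code in SAP Appendix 1 keeps separate SDs per arm, and the dose-response test in SAP 5.4 takes group-specific SEs. One study report would then carry two variance assumptions for the same endpoint, and a wide repeated-measures interval could be read as disagreement with the posterior.

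**Working it through.** **The plan's own figures.** The documents state no SE for this model. The Table 7 cell sizes (protocol 11.2) reproduce: 10/30 split 30:70 gives 3/9 and 7/21; split 40:60 it gives 4/12 and 6/18. The Table 7 Bayesian power cannot be reproduced exactly because the mixture components are not given, and it is not at issue here.

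**Inputs.** Suppressed subjects: SD 0.4 on placebo+NA, 2.16 on JNJ+NA (Table 7); 1:3 allocation (protocol 3.1); planned effect 1 log10 (protocol 11.2); fit by part against concurrent placebo (SAP 5.2.1, 5.2.1.1). Assumed: complete Week 24 data, unstructured matrix retained.

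**Formulas.** With complete data, a saturated visit-by-arm mean and a common unstructured matrix, the Week 24 variance estimate is the pooled variance (also confirmed numerically on simulated data).

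- Pooled variance: sp² = [(nS−1)sS² + (nE−1)sE²] / (nS+nE−2)
- Shared SE = √[sp²(1/nS + 1/nE)]
- Arm-specific SE = √(sS²/nS + sE²/nE)

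At 10/30: sp² = (9×0.16 + 29×4.6656)/38 = 136.742/38 = 3.598. Shared SE = √(3.598×0.1333) = 0.693. Arm-specific SE = √(0.0160 + 0.1555) = 0.414. Ratio 1.67.

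| Suppressed, nS/nE | Shared SE | Arm-specific SE | Ratio | 95% half-width, shared (pooled t) | 95% half-width, arm-specific (Satterthwaite) |
|---|---|---|---|---|---|
| 3/9 | 1.29 | 0.76 | 1.71 | 2.88 | 1.70 |
| 7/21 | 0.83 | 0.50 | 1.68 | 1.71 | 1.02 |
| 10/30 | 0.69 | 0.41 | 1.67 | 1.40 | 0.84 |

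The 10/30 row leaves out the HBeAg term of the pooled model, which costs one degree of freedom.

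**Sensitivity to the JNJ+NA SD.** With placebo SD held at 0.4, the ratio is about 1.5 at SD 1.0, 1.2 at SD 0.6 and 1.0 at SD 0.4.

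**Currently untreated subjects.** The monotherapy arm joins the pool and its SD is not given, so I assume 0.4 to 2.16. At 4/12/12 with monotherapy SD 0.4: sp² = (3×0.36 + 11×4.6656 + 11×0.16)/25 = 2.17, shared SE 0.85, arm-specific 0.69, ratio 1.23. At 6/18/18 with SD 2.16: 0.95 against 0.53, ratio 1.78. The other combinations lie between these.

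**Monotherapy versus JNJ+NA.** The small placebo variance now pulls the pooled value down. The ratio is 0.93 to 0.95 at planned sizes, so this interval is slightly too narrow. I give no Part A figure: for the 75 mg monotherapy arm, "this treatment arm was discontinued early per Protocol Amendment 4", so its Week 24 numbers are unknown.

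**Last fallback.** AR(1) averages variance over Weeks 1, 2, 4, 8, 12, 16, 20 and 24. If SD grows with the square root of time, the SD factor is √[(87/8)/24] = 0.67, and the suppressed ratios fall to 1.13–1.15. If SD is constant over time they do not change.

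**The case against.** The protocol leaves statistical detail to the SAP and lists this model under other analyses. The Bayesian posterior is its main evaluation, and no formal hypothesis is tested. All of that stands and limits the harm to interpretation. It does not license reversing a stated property of the model without saying so.

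The 1.7 rests on an SD of 2.16, which is a planning assumption. Protocol 1.1 reports no notable HBsAg change over 28 days in Phase 1, so the real SD may be smaller. That also stands: the mismatch is certain, its size is conditional.

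Arm-specific intervals are not a cure-all. In 100,000 simulated trials with assumed mixtures of 20–30% responders (matched to mean −1.05 and SD 2.16), coverage of nominal 95% intervals, shared versus arm-specific, was 87–92% versus 88–90% at 3/9, 97% versus 92% at 7/21 and 98% versus 93% at 10/30. The case for the change is precision and consistency with the protocol, not better coverage.

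Two stronger readings are tempting. A reader might infer a raised false-positive risk for JNJ+NA versus placebo+NA. At the planned SDs and allocation the SE is too large, so the error runs the other way. A reader might also infer from SAP section 5 ("Placebo treatments can be pooled as") that the choice between concurrent and pooled placebo is open for this model. That sentence is a general permission; SAP 5.2.1 and 5.2.1.1 fix the fit by part with the concurrent control.

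**Conclusion.** The departure from protocol 11.3.3 is plain from the text and should be corrected. In virologically suppressed subjects the shared covariance inflates the SE of JNJ+NA versus placebo+NA by about 1.7. That holds at the Table 7 SDs, fitted by part, with complete Week 24 data and the unstructured matrix kept. At 10/30 and the planned effect of 1 log10, the shared interval would include zero (half-width 1.40) and the arm-specific one would not (0.84); in the separate HBeAg cells both would include it. In untreated subjects the ratio is 1.23–1.78, depending on an unstated monotherapy SD.

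It would be wrong to read 1.7 as a fixed property of the analysis, since it falls to 1.0 if the arms turn out equally variable. It would also be wrong to say the trial's main efficacy conclusion is compromised: the Bayesian model and the dose-response test already use arm-specific variances, and SDs and SEs are tabulated by arm.

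**What to change.** Restore an arm-specific covariance in SAP 5.2.1.1 and Appendix 3, for both the HBeAg cells and the HBeAg-pooled model: a group term on treatment and no random intercept shared across arms. Choose a structure that 3–10 controls can support. An arm-specific unstructured matrix needs 36 parameters per arm over eight visits, which 3–7 controls cannot. One example is `repeated avisitn / type=ANTE(1) subject=usubjid group=trtlon`, since ANTE(1) is already the first fallback. It is only an example, because it has not been tried in SAS, with Kenward-Roger degrees of freedom, or on skewed data. In a limited check with separate REML code it converged in 62–90% of runs with 3 controls and in at least 99.7% with 6 or more.

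For that reason, name a Week 24 unequal-variance (Satterthwaite) comparison as the fallback. SAP 5.2.1.3 plans that "a similar analysis but without historical data in a frequentist approach will also be conducted as a sensitivity analysis" but is silent on variances; say that it uses separate ones.

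If a shared covariance is intended, record it as a departure from protocol 11.3.3 and give the reason.

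Cost: SAP wording and code only, with no change to data or conduct. The price is a simpler correlation structure than unstructured, intervals that lean on few controls and may cover below 95% with skewed data, and a Week 24 fallback that ignores earlier visits.
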